Appendix A Schedule of Procedures (Continued)

- ⁸ Height at Screening only
- 9 Patients who terminate treatment or post-treatment early from the study should be encouraged to participate in an early termination visit, at which time the Study D85 or Study D169 assessments should be conducted, respectively
- ¹⁰ Home Healthcare assessments and procedures may be conducted by a Home Healthcare professional at specified visits and as arranged by the site staff. If 3 consecutive Home Healthcare visits have been conducted, the Sponsor must be consulted prior to the scheduling of a 4th in-home visit
- ¹¹ 24-hr ABPM should take place after the visit 1 Screening labs have been resulted and the results are deemed not to be exclusionary. Ensure sufficient time during the Screening Period to allow for a repeat (if the first 24-hr monitoring is not successful) prior to the Study Day 1 visit
- ¹² Study Drug may be administered by a trained Home Healthcare Professional
- ¹³ For patients who have been administered 8 or more doses of Study Drug, a 24-hr ABPM should ideally be initiated in-clinic after all study procedures have been completed either on Study D78 or Treatment Early Termination/Study D85. If a repeat is necessary, the 24-hr ABPM should be initiated no later than the Study D92 visit. Ensure the 24-hr APBM is not done concurrently with other study procedures
- ¹⁴ The study visit must occur in-clinic if the 24-hour ambulatory blood pressure is initiated
- ¹⁵ Ideally should be completed prior to any interventional study procedures (e.g., blood draws, vital signs)
- ¹⁶ Urine angiotensinogen is not required at Screening

Time (time is in reference to Study Drug (ISIS 757456 or placebo) administration)

- a Pre-dose
- ^b Pre-dose, optional 2-hr post-dose

APPENDIX B. LIST OF LABORATORY ANALYTES

Appendix B List of Laboratory Analytes

Based on emerging data from this or future studies, additional tests not listed below may be performed on stored samples to better characterize the profile of ISIS 757456 or other similar oligonucleotides.

Plasma PK samples may also be used for profiling of drug binding proteins, bioanalytical method validation purposes, stability assessments, metabolite assessments, or to assess other actions of ISIS 757456 with plasma constituents

² Will be performed on abnormal findings unless otherwise specified

³ May be analyzed

APPENDIX C. PK SAMPLING SCHEDULE

Appendix C PK Sampling Schedule

PK Sampling Schedule

Study Day	D1	D8	D15	D22	D29	D36	D43	D50	D57	D64	D71	D78	D85	D92	D106	D120	D148	D169
to Dose of Study	Pre-dose, optional 2 hrs post-D1 SC injection		Pre- dose		Pre- dose		Pre- dose		Pre- dose		dose	Pre-dose, optional 2 hrs post-D78 SC injection	Anytime	Anytime	Anytime	Anytime	Anytime	Anytime
Number of Samples Collected	2		1		1		1		1		1	2	1	1	1	1	1	1

SC = subcutaneous

D = Day

APPENDIX D. GRADING SCALE FOR ADVERSE EVENTS RELATING TO LABORATORY ABNORMALITIES

Appendix D Grading Scale for Adverse Events Relating to Laboratory Abnormalities

The following grading recommendations for adverse events relating to lab test abnormalities are based upon the Common Terminology Criteria for Adverse Events (CTCAE) Version 5.0, November 2017.

Adverse Event	Mild	Moderate	Severe		
		Hematology	5		
aPTT prolonged	>ULN - 1.5 x ULN	>1.5 - 2.5 x ULN	>2.5 x ULN; bleeding		
Eosinophils increased'	>ULN and >Baseline	150	Steroids Initiated		
Fibrinogen decreased	<1.0 - 0.75 x LLN; if abnormal, <25% decrease from baseline	<0.75 - 0.5 x LLN; if abnormal, 25 - <50% decrease from baseline	<0.5 x LLN; if abnormal, ≥50% decrease from baseline		
Hemoglobin decreased (Anemia)	Hemoglobin (Hgb) <lln -="" 10.0="" dl;
<lln -="" 100="" 6.2="" <lln="" g="" l;="" l<="" mmol="" td="">Hgb <10.0 - 8.0 g/dL; <6.2 - 4.9 mmoVL; <100 - 80g/L	Hgb <8.0 g/dL; <4.9 mmol/L; <80 g/L; transfusion indicated	</lln></lln>	Hgb <10.0 - 8.0 g/dL; <6.2 - 4.9 mmoVL; <100 - 80g/L	Hgb <8.0 g/dL; <4.9 mmol/L; <80 g/L; transfusion indicated		
Hemoglobin increased**	Increase in >0 - 2 g/dL above ULN or above baseline if baseline is above ULN	Increase in >2 - 4 g/dL above ULN or above baseline if baseline is above ULN	Increase in >4 g/dL above ULN or above baseline if baseline is above ULN		
INR increased	>1.2 - 1.5; >1 - 1.5 times above baseline if on anticoagulation	>1.5 - 2.5; >1.5 - 2.5 x baseline if on anticoagulation; monitoring only indicated	>2.5; >2.5 x baseline if on anticoagulation; dose adjustment indicated		
Lymphocyte count decreased	<lln -="" 800="" mm3; <lln -="" 0.8="" 109/L</lln></lln>	<800 - 500/mm³; <0.8 - 0.5 × 10° /L	<500 /mm³; <0.5 x 10° /L		
Lymphocyte count increased	-	>4000/mm³ - 20,000/mm³	>20,000/mm ³		
Neutrophil count decreased	<lln -="" 1500="" mm3; <lln -="" 1.5="" 109 /L</lln></lln>	<1500 - 1000/mm³; <1.5 - 1.0 x 10° /L	<1000/mm³; <1.0 x 10° /L		
Platelet count decreased	<lln -="" 75,000="" mm³;
<lln -="" 10°="" 75.0="" l<="" td="" x="">	</lln></lln>				
White blood cell decreased	<lln -="" 3000="" mm3; <lln -="" 109 /L</lln></lln>	<3000 - 2000/mm³; <3.0 - 2.0 x 10 ⁹ /L	<2000/mm³; <2.0 x 10° /L		
		Chemistry			
Acidosis	pH <normal, but="">=7.3</normal,>	-	pH <7.3		
Alanine aminotransferase increased	>ULN - 3.0 x ULN if baseline normal 1.5 - 3.0 x baseline if baseline abnormal	>3.0 - 5.0 x ULN if baseline normal >3.0 - 5.0 x baseline if baseline abnormal	>5.0 x ULN if baseline normal >5.0 x baseline if baseline abnormal		
Alkaline phosphatase increased	>ULN - 2.5 x ULN if baseline normal 2.0 - 2.5 x baseline if baseline abnormal	>2.5 - 5.0 x ULN if baseline normal >2.5 - 5.0 x baseline if baseline abnormal	>5.0 x ULN if baseline normal >5.0 x baseline if baseline was abnormal		
Alkalosis	pH >normal, but ≤7.5	-	pH >7.5		
Aspartate aminotransferase increased	>ULN - 3.0 x ULN if baseline normal 1.5 - 3.0 x baseline if baseline abnormal	>3.0 - 5.0 x ULN if baseline normal >3.0 - 5.0 x baseline if baseline abnormal	>5.0 x ULN if baseline normal >5.0 x baseline if baseline abnormal		
Blood bilirubin increased	>ULN - 1.5 x ULN if baseline normal >1.0 - 1.5 x baseline if baseline abnormal	>1.5 - 3.0 x ULN if baseline normal >1.5 - 3.0 x baseline if baseline abnormal	>3.0 x ULN if baseline normal >3.0 x baseline if baseline abnormal		
Cardiac troponin I increased	Levels above the upper limit of normal and below the level of myocardial infarction as defined by the manufacturer	-9	Levels consistent with myocardial infarction as defined by the manufacturer		

Adverse Event	Mild	Moderate	Severe		
Cardiac troponin T increased	Levels above the upper limit of normal and below the level of myocardial infarction as defined by the manufacturer	-	Levels consistent with myocardial infarction as defined by the manufacturer		
CD4 lymphocytes decreased	<lln -="" 500="" mm3; <lln -="" 0.5="" 109 /L</lln></lln>	<500 - 200/mm³; <0.5 - 0.2 x 10° /L	<200/mm³; <0.2 x 10° /L		
CPK increased*	>ULN - <6 ULN	6 - 10 x ULN	>10 x ULN		
Creatinine increased**	>ULN - 1.5 x ULN if baseline normal > 1.0 - 1.5 x baseline if baseline abnormal	>1.5 - 3.0 x ULN if baseline normal >1.5 - 3.0 x baseline if baseline abnormal	>3.0 x ULN if baseline normal >3.0 x baseline if baseline abnormal		
GGT increased	>ULN - 2.5 x ULN if baseline normal 2.0 - 2.5 x baseline if baseline abnormal	>2.5 - 5.0 x ULN if baseline normal >2.5 - 5.0 x baseline if baseline abnormal	>5.0 x ULN if baseline normal >5.0 x baseline if baseline abnormal		
Hypercalcemia	Corrected serum calcium of >ULN - 11.5 mg/dL; >ULN - 2.9 mmol/L; Ionized calcium >ULN - 1.5 mmol/L	Corrected serum calcium of >11.5 - 12.5 mg/dL; >2.9 - 3.1 mmol/L; lonized calcium >1.5 - 1.6 mmol/L; symptomatic	Corrected serum calcium of >12.5 mg/dL; >3.1 mmol/L; lonized calcium >1.6 mmol/L; hospitalization indicated		
Hyperglycemia ^{††}	Fasting glucose value ≥126 mg/dL (7.0 mmoVL)	Change in daily management to maintain fasting blood glucose <126 mg/dL (7.0 mmol/L); e.g. addition of oral antiglycemic agent; workup for diabetes	Insulin therapy initiated; hospitalization indicated		
Hyperkalemia	>ULN - 5.5 mmol/L	>5.5 - 6.0 mmol/L; intervention initiated	>6.0; hospitalization indicated		
Hypermagnesemia	>ULN - 3.0 mg/dL; >ULN - 1.23 mmol/L	tu .	>3.0 mg/dL; >1.23 mmol/L		
Hypematremia	>ULN - 150 mmol/L	>150 - 155 mmol/L; intervention initiated	>155 mmol/L; hospitalization indicated		
Hyperphosphatemia	Laboratory finding only and intervention not indicated	Noninvasive intervention indicated	Severe or medically significant but not immediately life-threatening; hospitalization or prolongation of existing hospitalization indicated		
Hyperuricemia	>ULN without physiologic consequences	-	>ULN with physiologic consequences		
Hypoalbuminemia	<lln -="" 3="" dl;
<lln -="" 30="" g="" l<="" td=""><3 - 2 g/dL; <30 - 20 g/L	<2 g/dL; <20 g/L	</lln></lln>	<3 - 2 g/dL; <30 - 20 g/L	<2 g/dL; <20 g/L		
Hypocalcemia	Corrected serum calcium of <lln -="" 1.0="" 2.0="" 8.0="" <lln="" calcium="" dl;="" ionized="" l;="" l<="" mg="" mmol="" td="">Corrected serum calcium of <8.0 - 7.0 mg/dL; <2.0 - 1.75 mmo/L; lonized calcium <1.0 - 0.9 mmo/L; symptomatic	Corrected serum calcium of <7.0 mg/dL; <1.75 mmol/L; lonized calcium <0.9 mmol/L; hospitalization indicated	</lln>	Corrected serum calcium of <8.0 - 7.0 mg/dL; <2.0 - 1.75 mmo/L; lonized calcium <1.0 - 0.9 mmo/L; symptomatic	Corrected serum calcium of <7.0 mg/dL; <1.75 mmol/L; lonized calcium <0.9 mmol/L; hospitalization indicated		
Hypoglycemia [‡]	≥54 mg/dL - <70 mg/dL ≥3.0 mmol/L - <3.9 mmol/L	<54 mg/dL (3.0 mmol/L) AND no assistance required to actively administer carbohydrates, glucagon, or take other corrective actions	Requires assistance of another person to actively administer carbohydrates, glucagon, or take other corrective actions		
Hypokalemia	<lln -="" 3.0="" l<="" mmol="" td="">symptomatic with <lln -="" 3.0="" l;
intervention indicated</lln>	<3.0 mmol/L; hospitalization indicated	</lln>	symptomatic with <lln -="" 3.0="" l;
intervention indicated</lln>	<3.0 mmol/L; hospitalization indicated		
Hypomagnesemia	<lln -="" 1.2="" dl;
<lln -="" 0.5="" mmovl<="" td=""><1.2 - 0.9 mg/dL; <0.5 - 0.4 mmol/L	<0.9 mg/dL; <0.4 mmol/L	</lln></lln>	<1.2 - 0.9 mg/dL; <0.5 - 0.4 mmol/L	<0.9 mg/dL; <0.4 mmol/L		
Hyponatremia	<lln -="" 130="" l<="" mmol="" td="">125-129 mmol/L and asymptomatic	125-129 mmoVL symptomatic; 120-124 mmoVL regardless of symptoms	</lln>	125-129 mmol/L and asymptomatic	125-129 mmoVL symptomatic; 120-124 mmoVL regardless of symptoms		
Hypophosphatemia	Laboratory finding only and intervention not indicated	Oral replacement therapy indicated	Severe or medically significant but not immediately life-threatening; hospitalization or prolongation of existing hospitalization indicated		
Lipase increased	>ULN - 1.5 x ULN	>1.5 - 2.0 x ULN; >2.0 - 5.0 x ULN and asymptomatic	>2.0 x ULN with signs or symptoms		
Serum amylase increased	>ULN - 1.5 x ULN	>1.5 - 2.0 x ULN; >2.0 - 5.0 x ULN and asymptomatic	>2.0 x ULN with signs or symptoms		

Adverse Event	Mild	Moderate	Severe			
		Urine				
Proteinuria						
Adults	1+ proteinuria; urinary protein ≥ULN - <1.0 g/24 hrs	2+ and 3+ proteinuria; urinary protein 1.0 - 3.4 g/24 hrs;	4+ proteinuria; Urinary protein ≥3.5 g/24 hrs;			
Children	-	Urine P/C (Protein/Creatinine) ratio 0.5 - 1.9	Urine P/C >1.9			
Hematuria	Asymptomatic; clinical or diagnostic observations only; intervention not indicated	Symptomatic; urinary catheter or bladder irrigation indicated	Gross hematuria; transfusion, IV medications or hospitalization indicated; elective invasive intervention indicated			
	Adverse	Events at the Injection Site				
Adverse events at the injection site**	An event at the injection site (e.g. erythema, tenderness, itching) that is easily tolerated by the subject and does not affect the subject's usual daily activities	- Persistent (>24 hours) pain, phlebitis or edema; OR - Lipodystrophy, hair growth or alopecia, OR - Prolonged (>1 month) hypo/hyperpigmentation	- Ulceration or necrosis; severe tissue damage; operative intervention indicated, OR - Any event at the injection site that is incapacitating			

3.2.2.	Subject Population Analyzed	15
3.2.3.	Handling of Missing Data	16

3.2.4.	Disposition of Subjects	16
3.2.5.	Demographic and Baseline Characteristics	16
3.2.6.	Protocol Deviations	17
3.2.7.	Stratification, Subsets, and Covariates	17
3.2.8.	Scoring of Questionnaires	18
3.3.	Primary Analysis	19
3.3.1.	Primary Efficacy Analysis	19
3.3.2.	Sample Size consideration	19
3.4.	Secondary Efficacy Analyses	19
3.4.1.	Secondary Efficacy Endpoints	19
3.4.2.	Multiplicity	20
3.4.3.	Interim Analysis	21
3.5.	Exploratory Analyses.	21
3.6.	Pharmacokinetic (PK) and Immunogenicity (IM) Analysis	22
3.6.1.	PK Analysis	22
3.6.2.	Pharmacokinetic/Pharmacodynamic Exposure-Response Analysis	23
3.6.3.	IM Analysis	24
3.7.	Safety Analyses	26
3.7.1.	Exposure	26
3.7.2.	Adverse Events	26
3.7.3.	Laboratory Measurements	28
3.7.4.	2.12.4 Vital Signs	29
3.7.5.	12-Lead Electrocardiograms (ECG)	30
3.7.6.	Prior and Concomitant Medications	30
4.	REFERENCES	30
APPEND	IX 1. EQ-5D HEALTH STATE INDEX SCORE DERIVATION ALGORITHM	31
	LIST OF TABLES	
Table 1:	Weight of EQ-5D-5L Response by Region	31
	LIST OF FIGURES	
Figure 1:	Testing Strategy illustration	21

REVISION HISTORY

Version No.	Effective Date	Summary of Changes
1.0	28 March 2022	New Document
2.0	1 July 2022	 Updated language for Section 3.5, Exploratory Analyses endpoints for PGI-C, PGI-S and POP-HSQ. Section 3.2.1, for the continuous endpoints, Van Elteren test with treatment and randomization stratification factor will be conducted if the data departs substantially from normality. Changed from rank ANCOVA to Van Elteren test.
		• Section 3.7.3, modified potassium (K) categories to "Absolute levels ≥ 5.5—< 6, confirmed"; "Absolute levels ≥ 6, confirmed". Removed Platelet count first category "Confirmed Platelet count > 100,000/mm³". Clarified local lab data will be included when derive confirmed abnormal results.

ABBREVIATIONS

In addition to the study glossary provided in the protocol, here are additional abbreviations provided for the study SAP.

Abbreviation	Definition
ABP	ambulatory blood pressure
ABPM	ambulatory blood pressure monitoring
AE	adverse event
AGT	angiotensinogen
ALP	alkaline phosphatase
ALT	alanine aminotransferase (SGPT)
ANCOVA	Analysis of Covariance
BMI	body mass index
BP	blood pressure
CI	confidence interval
CRF	case report form
CVD	cardiovascular disease
CSR	clinical study report
DBP	diastolic blood pressure
ECG	electrocardiogram
eCRF	electronic Case Report Form
eGFR	estimated glomerular filtration rate
EQ-5D-5L	EuroQoL-5 Dimension 5 Level
FAS	full analysis set
HTN	hypertension
LCRIS	Local cutaneous reaction at injection site
LLQ	lower limit of quantitation
MMRM	mixed models with repeated measures
PD	pharmacodynamic(s)
PGI-C	Patient Global Impression- Change
PGI-S	Patient Global Impression- Severity
PK	pharmacokinetic(s)
POP-HSQ	Power Over Pressure- Hypertension Specific Questionnaire
PPS	per protocol set
SAE	serious adverse event
SAP	statistical analysis plan
SBP	systolic blood pressure
SF-12	12-Item Short Form Survey
TEAE	treatment-emergent adverse event
UACR	urinary albumin/creatinine ratio
ULN	upper limit of normal

1. INTRODUCTION

This document provides a description of the study organization, study procedures, and the plan for the statistical analysis of the study data. Section 1 discusses study design, objectives, and endpoints; Section 2 provides the study procedures; Section 3 provides the detailed plan for the statistical analyses.

The purpose of this plan is to provide specific guidelines from which the analysis will proceed. Any deviations from these guidelines will be documented in the clinical study report (CSR).

Within this document, the terms 'patient' and 'subject' are both used to describe the individual who enrolls in this study.

[figure not shown]
1.1. Study Overview

This is a Phase 2, double-blind, randomized, placebo-controlled study of ISIS 757456 conducted in uncontrolled hypertensive patients on ≥ 3 antihypertensive medications. Eligible patients will be stratified based on a screening eGFR result (<60 vs. ≥ 60 mL/min/1.73 m2) and randomized to 1 of 2 dose cohorts in a 1:1 ratio (Cohort A (80 mg ISIS 757456 or placebo) or Cohort B (120mg ISIS 757456 or placebo)). Within each dose cohort, patients will be further randomized to receive ISIS 757456 or placebo in a 2:1 ratio. Patients will receive SC doses of Study Drug on Study Days 1, 8, 15, 22, 29, 36, 43, 50, 57, 64, 71, and 78 during treatment period. Patients will continue their antihypertensive medication regimen throughout the study. The patient is expected to maintain adequate hydration and a low sodium diet throughout the study. After the Treatment Period, all patients will then complete a 13-week Post-Treatment Period.

This study will be conducted at multiple centers in the United States. Approximately 150 patients are planned to be enrolled in this study. Study Drug (ISIS 757456 or placebo) injection volumes will be 0.8 mL or 1.2 mL for cohort A or Cohort B, respectively. All Study Drug injections will be administered by qualified personnel at the clinic or by a home healthcare professional (as arranged with the site staff and after appropriate training).

The study will consist of Screening, Treatment, and Post-treatment. The overall length of a subject's participation will be approximately 31 weeks (up to 6 weeks for Screening, a 12-week Treatment Period, and a 13-week Post-Treatment Evaluation Period).

The study design and treatment schema are depicted as follows:

1.2. Objectives

1.2.1. Primary Objective

To evaluate the effect of ISIS 757456 compared to placebo on seated automated office systolic blood pressure (SBP) from Baseline to Study Day 85 in uncontrolled hypertensive patients on ≥ 3 antihypertensive medications

1.2.2. Secondary Objectives

- To evaluate the effect of ISIS 757456 on plasma angiotensinogen (AGT) concentration at each scheduled visit in uncontrolled hypertensive patients on ≥ 3 antihypertensive medications
- To evaluate the effect of ISIS 757456 on 24-hour ambulatory blood pressure at scheduled visits in uncontrolled hypertensive patients on ≥ 3 antihypertensive medications
- To evaluate the effect of ISIS 757456 on seated automated office SBP at each scheduled visit in uncontrolled hypertensive patients on ≥ 3 antihypertensive medications
- To evaluate the effect of ISIS 757456 on seated automated office diastolic blood pressure (DBP) at each scheduled visit in uncontrolled hypertensive patients on ≥ 3 antihypertensive medications

1.2.3. Safety Objectives

To evaluate the safety and tolerability of ISIS 757456 in uncontrolled hypertensive patients on ≥ 3 antihypertensive medications

1.2.4. Exploratory Objectives

- To evaluate the effects of ISIS 757456 administered subcutaneously (SC) (e.g., angiotensin II, renin [Plasma renin activity (PRA); direct renin], urinary angiotensinogen) in uncontrolled hypertensive patients on ≥ 3 antihypertensive medications
- To evaluate the pharmacokinetics (PK) of ISIS 757456 (as total full-length ASO, including fully conjugated, partially conjugated, and unconjugated ISIS 757456) administered SC in uncontrolled hypertensive patients on ≥ 3 antihypertensive medications
- To evaluate potential PK/ pharmacodynamic (PD) correlation with relevant biomarkers and/or clinical endpoints
- To evaluate the effects of ISIS 757456 on patients reported quality of life outcomes

1.3. Endpoints

1.3.1. Primary Endpoint

Change in seated automated office SBP from baseline to Study Day 85

1.3.2. Secondary Endpoints

- Absolute levels and change and percent change in plasma AGT concentration from baseline to each scheduled, post-baseline visit
- Changes from Baseline to Study Day 85 in 24-hour mean SBP and DBP measured by ambulatory blood pressure monitoring (ABPM)
- Percentage of patients reaching the goals of seated automated office SBP ≤ 140 mmHg, DBP ≤ 90 mmHg, and both for each scheduled, post-Baseline visit (excluding patients with a baseline SBP of ≤ 140 mmHg)
- Percentage of patients reaching the goals of automated office seated SBP ≤ 130 mmHg, DBP ≤ 80 mmHg, and both for each scheduled, post-Baseline visit
- Change on seated automated office SBP from Baseline to each scheduled, post-Baseline visit
- Change on seated automated office DBP from Baseline to each scheduled, post-Baseline visit

1.3.3. Safety Endpoints

Incidence and severity of treatment-emergent adverse events (TEAE), use of concomitant medications, abnormal findings in laboratory assessments, electrocardiogram (ECG), and vital signs

1.3.4. Exploratory Endpoints

- Absolute levels and change and percent change of angiotensin II, renin (PRA; direct renin), urinary AGT concentration from Baseline to each scheduled, post-Baseline visit
- Summary of peak and trough ISIS 757456 plasma concentrations
- Potential exposure-response analysis using relevant exposure parameters and biomarkers including, but not limited to trough concentration (C_{trough}) and plasma AGT may be performed
- Changes from Baseline to Study Day 85 and each scheduled post-Baseline
 assessment in the following patient reported outcome questionnaires: EuroQol-5
 Dimension 5 Level (EQ-5D-5L), 12-Item Short Form Survey (SF-12), Power Over
 Pressure- Hypertension Specific Questionnaire (POP-HSQ), Patient Global
 Impression- Change (PGI-C), and Patient Global Impression-Severity (PGI-S)

- Change from Baseline to Study Day 85 in daytime SBP and DBP from 24 hr ABPM
- Change from Baseline to Study Day 85 in nighttime SBP and DBP from 24 hr ABPM
- o Change from Baseline to Day 85 in eGFR
- o Change from Baseline to Day 85 in urinary albumin/creatinine ratio (UACR)
- Primary endpoint, selective secondary and exploratory endpoints will be also analyzed using a sub-population of patients with baseline 24 hr ABPM SBP > 130

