1.2.4. Exploratory Endpoints

- Absolute levels and change and percent change of angiotensin II, renin (PRA; direct renin), urinary AGT from Baseline to each scheduled, post-Baseline visit
- Summary of peak and trough ISIS 757456 plasma concentrations
- Potential exposure-response analysis using relevant exposure parameters and biomarkers including, but not limited to trough concentration (C_{trough}) and plasma AGT may be performed
- Changes from Baseline to Study Day 85 and each scheduled post-Baseline assessment in the following patient reported outcome questionnaires: EuroQol-5 Dimension 5 Level (EQ-5D-5L), 12-Item Short Form Survey (SF-12), Power Over Pressure- Hypertension Specific Questionnaire (POP-HSQ), Patient Global Impression- Change (PGI-C), and Patient Global Impression- Severity (PGI-S)

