2.5.1. Benefit Assessment

This compound has been administered to healthy volunteers, hypertensive patients washed out of their antihypertensive medications, and hypertensive patients on antihypertensive medications. As a GalNAc, specifically due to the mediated uptake to the hepatocytes, ISIS 757456 will primarily affect circulating AGT rather than decrease renal AGT transcription. Therefore, it has the potential of an improved therapeutic index due to the potential of lower occurrence of hyperkalemia and ARF, which are issues with aggressive RAAS blockage in some subjects that may be due, in part, to excessive inhibition of intrarenal Ang II signaling. Based on its MOA of blocking the RAAS pathway it is expected to lower the BP in patients with HTN. While there are other compounds (ACEi, ARB, aldosterone blockers, renin inhibitors) that block different components of this pathway, this compound blocks AGT, the most upstream factor in the pathway. Finally, due to its estimated half-life of 2 to 4 weeks, ISIS 757456 may have a superior

duration of action compared to RAAS blockers thereby contributing to the potential of ISIS 757456 having an enhanced pharmacological benefit relative to the standard of care.

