3.5. Exploratory Analyses

The exploratory efficacy analyses will be conducted using statistical methods described in Section 3.2.1. ANCOVA model will be used for continuous endpoints, logistic regression model will be used for dichotomous endpoints using PPS and FAS.

- Comparison of absolute levels, change and percent change from baseline to each scheduled post-Baseline visit in angiotensin II, renin (Plasma renin activity [PRA]; direct renin), and urinary AGT will be conducted between each ISIS 757456-treated group and pooled-placebo group in the PPS and FAS.
- Comparison of absolute scores, change from baseline to each scheduled post-Baseline visit in SF-12 scores (8 domains, PCS, and MCS), and EQ-5D-5L (5 dimensions, VAS, and index score) will be conducted between each ISIS 757456-treated group and pooled-placebo group.

- Proportion of non-worsening from baseline to each scheduled post-Baseline PGI-C and PGI-S will be compared between each ISIS 757456-treated group and pooled-placebo group. PGI-C will be categorized by non-worsening and worsening, where non-worsening includes categories of "Much better", "A little better" and "No change". PGI-S will be categorized by non-worsening and worsening, where non-worsening defined as ≥ 0 point improvement in the change from baseline score. The adjusted odds ratio (each ISIS 757456-treated dose group vs. pooled-placebo group) with 95% CI from logistic regression model will be provided.
- Comparison of change from Baseline to Study Day 85 in daytime SBP and DBP from 24 hr ABPM will be conducted between each ISIS 757456-treated group and pooled-placebo group
- Comparison of change from Baseline to Study Day 85 in nighttime SBP and DBP from 24 hr ABPM will be conducted between each ISIS 757456-treated group and pooled-placebo group
- Comparison of change from Baseline to Day 85 in eGFR will be conducted between each ISIS 757456-treated group and pooled-placebo group
- Comparison of change from Baseline to Day 85 in UACR will be conducted between each ISIS 757456-treated group and pooled-placebo group
- Primary endpoint, selective secondary and exploratory endpoints will be also analyzed using a sub-population of patients with Baseline 24 hr ABPM SBP > 130
- POP-HSQ scores will be listed.

Additional POP-HSQ summaries and analysis will be conducted, details are described in POP-HSQ SAP. Other exploratory PK endpoints will be further described in the Section 3.6.

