3.7.3. Laboratory Measurements

Chemistry including thyroid panel and inflammatory, hematology, coagulation, and urinalysis (result, change and percent change from baseline) will be summarized by each treatment group and each post-baseline visit. Listing of laboratory assessments in Chemistry, Hematology and urinalysis will be provided. Local laboratory data will also be provided in the listings separately.

For alanine aminotransferase (ALT) and aspartate aminotransferase (AST), the number and percent of subjects with post-Baseline results falling in each of the following categories (using available central and local laboratory assessments) will be tabulated:

ALT or AST $> 3 \times ULN$, confirmed

ALT or AST $> 5 \times ULN$, confirmed

ALT or AST $> 3 \times$ ULN and serum total bilirubin $> 2 \times$ ULN, confirmed or INR > 1.5

ALT > 3 × ULN at any time during post-baseline or AST > 3 × ULN at any time during post-Baseline and with total bilirubin (TBL) > 2 × ULN at any time during post-baseline

For potassium (K), the number and percent of subjects falling in each of the following categories (using available central and local laboratory assessments) during post-baseline will be tabulated:

- Absolute levels $\geq 5.5 < 6$ mmol/L, confirmed
- Absolute levels \geq 6 mmol/L, confirmed

For platelet, the number and percentage of patients falling in each of the following categories (using available central and local laboratory assessments) based on post-baseline assessments will be provided:

- Confirmed Platelet count 75,000 to ≤ 100,000/mm³
- Confirmed Platelet count 50,000 to < 75,000/mm³
- Confirmed Platelet count 25,000 to < 50,000/mm³
- Confirmed Platelet count < 25,000/mm³
- Confirmed ≥ 30% Platelet count decrease from baseline; further classifying by the lower limit of normal (Above or below)

The number and percent of subjects with post-baseline results falling in the following categories (using available central and local laboratory assessments) will be also tabulated:

- Confirmed 30% decline in eGFR from Baseline eGFR values [eGFR should be calculated using the CKD-EPI creatinine equation (Levey et al. 2009)]
- Confirmed proteinuria: Absolute UPCR value ≥ 1000 mg/g

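### Urinary AGT is defined as a concentration with no stated correction for urine dilution; a creatinine ratio from the same sample would remove avoidable noise from this exploratory endpoint

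*Combined protocol and SAP*

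**What the plan says.** The protocol (1.2.4, Exploratory Endpoints) names "urinary AGT from Baseline to each scheduled, post-Baseline visit" and gives no unit or normalisation. SAP 1.3.4 makes it more specific: "urinary AGT concentration from Baseline to each scheduled, post-Baseline visit". SAP 3.5 then plans the comparison of level, change and percent change in angiotensin II, renin "and urinary AGT will be conducted between each ISIS 757456-treated group and pooled-placebo group in the PPS and FAS", using the general ANCOVA of SAP 3.2.1.

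Other urine proteins are handled differently. The same list in SAP 1.3.4 gives albumin as a ratio to creatinine. SAP 3.7.3 and Protocol 8.6.2 judge proteinuria by UPCR, with the category "Absolute UPCR value ≥ 1000 mg/g".

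On sampling, a footnote to the Urinalysis row of the Schedule of Procedures (Appendix A) says "Urine angiotensinogen is not required at Screening". No timed or 24-hour urine collection is visible in that schedule. Under the baseline definition in SAP 3.2.1, plasma AGT is averaged over all pre-dose values, while every other assessment takes the last non-missing pre-dose value. With no Screening sample required, the urinary AGT baseline will usually be one Day 1 sample.

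**The concern.** Concentration is a natural measure in plasma. In an untimed urine sample it equals the excretion rate divided by urine flow, so it moves with dilution even when AGT excretion does not. The plan avoids this for albumin and protein by dividing by creatinine, but states no such step for AGT.

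Hydration varies from day to day, and diuretics are an allowed background class (Protocol 5.1, criterion 6). One unusually dilute or concentrated Day 1 sample carries into every later change and percent change for that patient.

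Urinary AGT is the only listed AGT measure taken from urine. The rationale in Protocol 2.5.1 is that "ISIS 757456 will primarily affect circulating AGT rather than decrease renal AGT transcription", so readers of the report are likely to look at this endpoint with that claim in mind. A result blurred by dilution would be hard to interpret in either direction.

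**Working it through.** The documents give no figure for urinary AGT, so there is none to reproduce. The flow changes and SDs below are assumptions. Only the alpha (two-sided 0.05, SAP 3.2.1) and the 43 patients per group (SAP 3.3.2) come from the plan.

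**1. Noise in the change.** Concentration = (AGT/creatinine ratio) × (urine creatinine concentration). On the log scale, let e be the within-person SD of the ratio and d that of dilution, taken as independent. The variance of change is 2(d² + e²) for concentration and 2e² for the ratio, so the inflation is (d² + e²)/e².

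SAP 3.2.1 uses ANCOVA with baseline as covariate, which softens this. With between-person variance b² and s² the within-person variance, the residual variance is s²(2b² + s²)/(b² + s²). The last column uses b = 0.5, with s² = d² + e² for concentration and s² = e² for the ratio.

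| d | e | Inflation, raw change | Inflation, ANCOVA residual |
|---|---|---|---|
| 0.3 | 0.5 | 0.34/0.25 = 1.36 | 0.484/0.375 = 1.29 |
| 0.5 | 0.5 | 0.50/0.25 = 2.00 | 0.667/0.375 = 1.78 |
| 0.5 | 0.3 | 0.34/0.09 = 3.78 | 0.484/0.156 = 3.10 |

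Confidence intervals widen by the square root of the last column: about 1.14-, 1.33- and 1.76-fold. A negative correlation between the ratio and dilution would make the inflation smaller.

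**2. False change if dilution shifts.** With excretion fixed and urine flow multiplied by f, concentration changes by 1/f − 1.

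- f = 0.9: +11.1%
- f = 1.1: −9.1%
- f = 1.2: −16.7%
- f = 1.3: −23.1%
- f = 1.5: −33.3%

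The AGT/creatinine ratio changes by 0% for any f, provided creatinine excretion is unchanged.

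**3. Effect on the comparison with placebo.** If flow shifts equally in both arms, the chance of p < 0.05 with no true change in excretion stays at 5%. If it shifts only on active drug, the noncentrality is ln(f)/(SD × √(2/43)) with 84 degrees of freedom. For f = 1.2 and SD of log change 0.5, this is 0.182/(0.5 × 0.2157) = 1.69. The chance of p < 0.05 is then:

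| Flow on active drug only | SD 0.5 | SD 0.8 | SD 1.0 |
|---|---|---|---|
| ×1.0 | 5% | 5% | 5% |
| ×1.1 | 14.1% | 8.5% | 7.2% |
| ×1.2 | 38.7% | 18.1% | 13.3% |
| ×1.3 | 67.2% | 32.4% | 22.5% |

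The (d, e) pairs in step 1 imply an SD of log change of √(2 × 0.34) = 0.82 or √(2 × 0.50) = 1.0. The last two columns are therefore the ones consistent with step 1; the SD 0.5 column needs smaller within-person variation.

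**The case against.** The strongest objection is that much rests on one word. The protocol and SAP 3.5 both say only urinary AGT. The SAP also added the word concentration to plasma AGT, which suggests general rewording rather than a decision against normalising. Urinary AGT sits in the Urinalysis row, whose analytes are in Appendix B, and that analyte table is missing from the text available. A ratio listed there cannot be excluded. This stands as a limit, but if Appendix B does list a ratio, SAP 1.3.4 still needs rewording to match.

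A reader might infer that diuretics and hydration advice bias the comparison with placebo. The documents do not support that. The antihypertensive regimen is to be kept stable (Protocol 5.1, criterion 6), and hydration advice begins at Screening and continues in all arms of a blinded trial. These factors mainly add noise.

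A reader might also infer that a drug-induced diuresis will pass for suppression of renal AGT. No passage reports that the drug changes urine volume. Protocol 2.2 only ties Ang II to sodium reabsorption and aldosterone secretion, and Protocol 2.3.4 says Phase 1 did not result in renal changes. Diuretics are named among possible responses to raised potassium (Protocol 8.5.4 and 8.6.5), so use after randomisation could differ by arm. The PPS excludes patients who altered antihypertensive medication before Day 85, so this route would bear mainly on the FAS and later visits. Nor do the documents say that urinary AGT will be read as renal AGT, and a creatinine ratio would not separate filtered plasma AGT from AGT of renal origin.

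Finally, the ratio could be added later and explained in the study report. It could, but choosing between two forms after unblinding is weaker than fixing the main form beforehand.

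**Conclusion.** The point holds as a better choice of method for one exploratory endpoint. As worded, the SAP analyses a dilution-dependent concentration from a single-sample baseline, while its other urine protein measures use creatinine ratios. The expected cost is lost precision: roughly 1.3- to 3.1-fold residual variance under ANCOVA, or 1.4- to 3.8-fold for raw change, under the assumed SDs and independence.

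Bias against placebo is conditional on dilution differing by arm. This is possible but undocumented, and the false-positive percentages illustrate that condition; they do not predict it. The conclusion also assumes untimed samples and no ratio specified in Appendix B. The endpoint lies outside the testing sequence in SAP 3.4.2, so no sample size, power, alpha, primary or key secondary result changes.

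**What to change.** In SAP 1.3.4 and 3.5, make the urinary AGT/creatinine ratio, using creatinine from the same urine sample, the main form of this endpoint for level, change and percent change. Keep raw urinary AGT concentration as a supportive analysis, so that nothing already planned is lost. State the type of urine sample, and align the wording with the analyte list in Appendix B.

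The cost is a wording change and one derived variable. UPCR and UACR already require urine creatinine, so no new sample should be needed; confirm that creatinine is reported at each visit with urinary AGT. The downside is that the ratio also reflects differences in creatinine excretion between patients. These largely cancel in within-patient change, but remain in comparisons of absolute level.
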